Official Title:

Evaluation of the Effects of Subspinal Le Fort and Conventional Le Fort I Osteotomy on Nasolabial Soft Tissues

NCTNumber:

NCTXXXXXXXXX

Not yet assigned

Document Date:

January 2021

DocumentType:

Study Protocol

Statistical Analysis Plan

Study Design

This controlled clinical study was designed as a single-center, prospective, randomized, and double-blind trial.

All volunteers will be informed about the medications to be used in the study, possible side effects, the surgical procedure, and potential complications, and their informed consent will be obtained.

The present study will investigate the potential differences in nasal soft tissue changes associated with the modification of subspinal osteotomy compared to the conventional technique used in Le Fort I osteotomy, without making any changes to the routine orthognathic surgery and postoperative follow-up protocols conducted in our clinic.

Selection Criteria

Volunteers will be selected from patients presenting to our clinic with functional, aesthetic, and phonation complaints due to skeletal orthodontic anomalies and who are scheduled to undergo Le Fort I and/or Bilateral Sagittal Split Osteotomy under general anesthesia.

Participants will be divided into two groups according to the osteotomy technique. From both groups, a total of 30 patients aged between 18–40years, without acute infection, with ASA I–II classification, no systemic disease, no history of hypersensitivity to any medication, normal hemoglobin levels (female: 12–14 g/dL; male: 14–16 g/dL), INR <1.5, and no history of NSAID use within one week prior to surgery will be included.

Patients with ASA III or higher physical status, hepatic or renal dysfunction, neuropathic disease, long-term NSAID or opioid use, a history of drug allergy, preoperative pain, swelling or inflammation in the head and neck region, and those who are pregnant or breastfeeding will be excluded from the study.

A total of 30 patients included in the study will be randomly divided into two groups (n=15 each):

- Group I: Subspinal Le Fort I osteotomy group (n=25)
- Group II Conventional Le Fort I osteotomy group (n=25)

Before the operation, all patients will be informed about the type of osteotomy to be performed and the use of 3D photography for postoperative edema assessment.

Patients will complete the ROE (Rhinoplasty Outcome Evaluation) scale preoperatively and at 6 months postoperatively to provide a subjective evaluation of their aesthetic and functional outcomes.

To ensure consistency between preoperative and postoperative imaging, craniocervical angle measurements will be performed, and only images without statistically significant differences will be included. Changes in maxillary position (anterior and/or superior movement) and their effects on nasal tissues will be analyzed.

Preoperative and postoperative measurements will be performed twice by a single researcher at two-week intervals using dedicated software, and the mean values will be recorded.

Maxillary movements at Point A (Pt A), posterior nasal spine (PNS), incisor superius (Is), and anterior nasal spine (ANS) will be evaluated in the X, Y, and Z coordinate system (X-axis: transverse, Y-axis: sagittal, Z-axis: vertical) following conventional or subspinal Le Fort I osteotomy.

The following anatomical landmarks will be identified: alar (Al), alar curvature (Ac), soft tissue glabella (Gs), soft tissue nasion (Ns), pronasale (Prn), columella (Cm), subnasale superior (Sns), subnasale (Sn), and labrale superior (Ls).

The following measurements will be performed:

1. Nasal width
 2. upper lip length
 3. Alar base width
 4. columellalobular angle
 5. Nasal tip angle
 6. Nasolabial angle
 7. Nostril width
-
-

Postoperative Edema Assessment

Postoperative edema will be evaluated using the 3dMD three-dimensional imaging system.

3D images will be obtained at the following time points:

- Preoperative day 1 (T0)
- Postoperative day 1 (T1)
- Postoperative day 3 (T2)
- Postoperative day 7 (T3)
- Postoperative month 1 (T4)
- Postoperative month 3 (T5)
- Postoperative month 6 (T6)

Images will be captured with patients in maximum intercuspation, with relaxed lips and open eyes. All images will be obtained by the same clinician.

Rhinoplasty outcome evaluation (roe scale)

The Rhinoplasty Outcome Evaluation is a patient-reported outcome measure designed to assess satisfaction with nasal appearance and function following rhinoplasty.

Measurement:

It consists of 6 questions, each scored from 0 (most negative) to 4 (most positive); the total score is summed, divided by the maximum possible score (24), and multiplied by 100 to yield

a percentage score ranging from 0 to 100, where higher scores indicate greater patient satisfaction.

Processing of 3D Images

Anatomical landmarks will be identified on 3D images to superimpose preoperative and postoperative scans. Six reference points will be used: bilateral medial and lateral canthi (four points), nasion, and trichion.

Images will be superimposed, and volumetric analyses will be performed using 3dMD Vultus Software (3dMD, Atlanta, GA, USA).

Statistical Analysis

All statistical analyses will be performed using SPSS 22.0 (SPSS Inc., Chicago, IL, USA).

Descriptive statistics (mean, standard deviation, minimum, maximum) will be used to define continuous variables. Normality of data distribution will be assessed using the Shapiro–Wilk test.

Comparisons between groups will be performed using one-way ANOVA and Tukey post hoc analysis.

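### The eligibility text does not require a Le Fort I, so a BSSO-only patient qualifies as written, and Selection Criteria gives two opposite orders for eligibility and group formation

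*Combined protocol and SAP*

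**What the plan says.** **Who may enter.** Selection Criteria draws volunteers from clinic patients "scheduled to undergo Le Fort I and/or Bilateral Sagittal Split Osteotomy under general anesthesia". It then lists age, infection, ASA class, systemic disease, hypersensitivity, haemoglobin, INR and recent NSAID use. The exclusion list begins "Patients with ASA III or higher physical status, hepatic or renal dysfunction, neuropathic disease, long-term NSAID or opioid use, a history of drug allergy" and goes on to preoperative pain, swelling or inflammation in the head and neck, pregnancy and breastfeeding. None of these items concerns which jaw is to be operated on.

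**What is compared.** Both groups are Le Fort I techniques, subspinal and conventional. The measurement paragraphs after Selection Criteria assess maxillary movement after one or other of these two techniques.

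**In what order.** Selection Criteria first says: "Participants will be divided into two groups according to the osteotomy technique". The next sentence applies the criteria: "From both groups, a total of 30 patients aged between 18–40years, without acute infection, with ASA I–II classification, no systemic disease", and so on through the list, are to be included. After the exclusions it says: "A total of 30 patients included in the study will be randomly divided into two groups (n=15 each").

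**How oedema is analysed.** Oedema is assessed from 3D images before surgery and at six times after it, from day 1 to month 6. Statistical Analysis compares the groups by one-way ANOVA with Tukey post hoc tests and names no covariate or stratification factor.

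**The concern.** The and/or wording covers three kinds of patient: Le Fort I alone, Le Fort I with BSSO, and BSSO alone. The third kind can receive neither study technique and has no Le Fort I movement to analyse. If such a patient were randomised, there would be two poor choices: keep the patient, which pulls the estimated difference between techniques toward zero, or remove the patient after randomisation.

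The order of eligibility and allocation matters because randomisation protects the comparison only if the decision to include a patient is made before the group is known. Text that forms the groups first and then picks eligible patients out of them would permit selection with the group in view. The document describes neither how the allocation sequence is generated nor how it is concealed, so nothing elsewhere settles which order applies.

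The same wording also mixes one-jaw and two-jaw surgery. If BSSO adds to the measured swelling, which the document does not state, the mix adds variation to the oedema outcome, and the planned ANOVA leaves it in the error term.

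**Working it through.** **1. Eligibility, read item by item.**

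| Text | Does it require a Le Fort I? |
|---|---|
| Source-population sentence | No; BSSO alone satisfies it |
| Inclusion items | No |
| Exclusion items | No |
| Title, study question, group names | Presuppose it, but are not criteria |
| Maxillary movement measurements | Presuppose it, but are not criteria |

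The source-population sentence is the only one that states planned surgery as a condition of entry, and it leaves BSSO alone inside.

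**2. Order, sentences side by side.**

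| Sentence | First step | Second step |
|---|---|---|
| Division by technique, then 30 taken from both groups | Groups formed | Criteria applied |
| The 30 included patients randomly divided | Patients included | Groups formed |

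Read literally, the two cannot both hold.

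**3. Size of possible dilution (illustration only).** The plan gives no alpha, power, effect size or standard deviation, so it has no power figure to reproduce. All inputs below except n are assumed:

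- n = 15 per group, as in the text. The group list gives 25 per group; that conflict is a separate matter.
- Two-sided alpha 0.05, two-sample t-test, equal standard deviations.
- A true standardised difference d that gives 80% power when every patient has a Le Fort I. For n = 15 this is d = 1.06.
- k BSSO-only patients in each group, with zero technique effect and the same standard deviation.

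Diluted difference = d × (1 − k/15).

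| k per group | 1 − k/15 | Diluted d | Power |
|---|---|---|---|
| 0 | 1.000 | 1.06 | 80% |
| 1 | 14/15 = 0.933 | 0.99 | 74% |
| 2 | 13/15 = 0.867 | 0.92 | 68% |
| 3 | 12/15 = 0.800 | 0.85 | 61% |

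With 25 per group, d reset to give 80% power and the same fractions diluted, the powers are again 74%, 68% and 61%. The conflict over group size therefore does not affect the illustration.

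**4. Cost of the covariate.** With 30 patients and two groups, a comparison at one time point has 30 − 2 = 28 residual degrees of freedom. Adding a yes/no term leaves 30 − 3 = 27.

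**The case against.** The strongest reply is that the and/or sentence describes the pool from which volunteers come, not the final entry rule. The title, the study question, both group names and the maxillary measurements all presuppose a Le Fort I, and it is hard to see anyone randomising a patient between two versions of an operation that is not planned. This stands as far as intent goes. A reader might infer from the and/or wording that BSSO-only patients will be enrolled; the document does not support that. It does not remove the gap, because no criterion turns the intent into a rule.

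On order, the phrase about both groups can be read as a combined headcount of 30, and the later sentence plainly puts inclusion before random division. This also stands in part. A reader might infer that the trial plans to select patients after allocation, or is not randomised at all. The text supports only that two sentences conflict and that one of them would permit it.

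On two-jaw surgery, accepting both kinds of case fits the stated aim of leaving routine surgery unchanged. A reader might infer that unequal numbers of two-jaw cases would bias the oedema comparison. Under randomisation, such an imbalance arises by chance: it costs precision and can shift a single result, but it is not systematic bias. Nor does the document say which facial region the volumetric analysis covers, so the contribution of BSSO to the measured swelling has to be assumed.

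Finally, the power figures rest on assumed inputs and say nothing about how many BSSO-only patients this trial would meet. That is correct, and they are offered on that footing.

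**Conclusion.** The point holds as a defect of the written rule and should be fixed. Two things follow from the text alone, with no assumption: the criteria do not require a Le Fort I although both study techniques are Le Fort I techniques, and Selection Criteria gives two opposite orders for eligibility and group formation. The numerical consequence depends on how many BSSO-only patients would be randomised. That number is not given and may be zero, in which case there is no dilution. The case for adjusting the oedema analysis is weaker: it rests on the assumption that BSSO affects the measured swelling, and its purpose is precision and protection against chance imbalance.

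**What to change.** 1. In Selection Criteria, make a planned Le Fort I osteotomy, with or without BSSO, an explicit condition of entry.
2. Delete the phrase that draws the 30 patients from both groups, together with the preceding division by technique. State once that patients who meet all criteria and have consented are then randomised 1:1 to the subspinal or the conventional technique.
3. In Statistical Analysis, replace the unadjusted one-way ANOVA for oedema with a linear model of group adjusted for planned concomitant BSSO (yes/no), recorded before randomisation.

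The first two are wording changes. Patients scheduled for BSSO alone would no longer count toward recruitment, but they carry no information on the technique comparison. The third changes the planned analysis and should be recorded as such. It uses one degree of freedom and brings little benefit if BSSO turns out to have little effect on the measured volume.

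### Patients with and without a mandibular osteotomy (BSSO) are pooled in an unadjusted comparison of a 3D volume with no set region, which can cost power for the oedema outcome without biasing it

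*Combined protocol and SAP*

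**What the plan says.** - **Population (Selection Criteria).** Volunteers are those "who are scheduled to undergo Le Fort I and/or Bilateral Sagittal Split Osteotomy under general anesthesia". A Le Fort I alone and a Le Fort I with BSSO both qualify, and no exclusion removes the mix. Read literally, BSSO-only patients would also qualify; that is a separate matter and is set aside here.
- **Grouping and allocation (Selection Criteria).** "Participants will be divided into two groups according to the osteotomy technique". The split is "A total of 30 patients included in the study will be randomly divided into two groups (n=15 each"). No stratification, blocking or minimisation is mentioned. The group lines give a different size: "Group I: Subspinal Le Fort I osteotomy group (n=25") and "Group II Conventional Le Fort I osteotomy group (n=25").
- **Oedema outcome (Postoperative Edema Assessment; Processing of 3D Images).** 3dMD images are taken before surgery, on days 1, 3 and 7, and at months 1, 3 and 6. "Images will be superimposed, and volumetric analyses will be performed using 3dMD Vultus Software". The six points named there (four canthi, nasion, trichion) register the scans to each other and do not enclose a measured volume.
- **Analysis (Statistical Analysis).** One-way ANOVA with Tukey comparisons. No covariate, stratum or subgroup for BSSO is given.
- **Other outcomes.** The seven listed linear and angular measurements all concern the nose or upper lip. No outcome is named as primary.

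**The concern.** The trial compares two ways of cutting the maxilla, and its stated interest is nasal soft tissue. A BSSO is a second osteotomy, in the mandible, and can be expected to cause swelling of its own. That swelling carries no information about the maxillary technique. If the measured volume reaches the lower face, it enters the oedema comparison in two ways:

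- It widens the spread within each arm, whatever the balance between arms.
- If chance gives one arm more two-jaw operations, it moves the difference between arms up or down.

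Both effects should be largest on days 1, 3 and 7. What is at stake is mainly a real difference in oedema being missed. The planned one-way model cannot remove either effect, because it has no place for the type of operation.

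**Working it through.** **Inputs from the document.** 15 per arm (25 in the group lines); two arms; one-way ANOVA, which with two arms is the two-sample t-test.

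**Inputs assumed.** The document gives no BSSO share *q*, no BSSO effect on volume *B* (in SDs among patients having the same operation), no alpha and no power. I use *q* = 20–80%, *B* = 0.5–2, two-sided alpha 0.05 and 80% power, and I suppose that the volume includes the lower face.

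**1. The plan's own figure.** The sample size cannot be reproduced, as it has no stated basis. For scale, the difference detectable with 80% power is (1.960 + 0.842) × √(2/n): 2.802 × 0.365 = 1.02 SD at 15 per arm and 2.802 × 0.283 = 0.79 SD at 25. The simulations below use 1.06 SD, which gives 80% power with the t-test at 15 per arm.

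**2. Added variance.** Total SD = √(1 + q(1 − q)B²). At *q* = 50%:

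| B | Total SD | BSSO share of variance | Power, normal formula | Power, simulated, unadjusted | Power, simulated, adjusted |
|---|---|---|---|---|---|
| 0 | 1.00 | 0% | 80% | 80% | 78–79% |
| 0.5 | 1.03 | 6% | 78% | 77–78% | 78–79% |
| 1 | 1.12 | 20% | 71% | 70% | 78–79% |
| 2 | 1.41 | 50% | 51% | 50% | 78–79% |

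The variance share is 0.25B²/(1 + 0.25B²); for *B* = 1 it is 0.25/1.25 = 20%. The simulated columns average over all random splits at 15 per arm with simple allocation. Adjusted means arm plus type of operation in the model. The first row shows the price of adjusting for a factor that does nothing: about 1.5 points of power. At *B* = 0.5 the gain is negligible. At a 20% or 80% share the loss is smaller: the normal formula gives 74% at *B* = 1 and 59% at *B* = 2. At 25 per arm the proportionate loss is the same for an effect of 0.79 SD.

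**3. Chance imbalance (exact hypergeometric).**

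| BSSO share | At least 20 points apart, 15/arm | At least 33 points apart, 15/arm | At least 20 points apart, 25/arm | At least 33 points apart, 25/arm |
|---|---|---|---|---|
| 50% | 47% | 14% | 26% | 2% |
| 60% | 26% | 6% | 15% | 1% |
| 70% | 43% | 11% | 22% | 1% |
| 80% | 17% | 2% | 7% | 0.1% |

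The values rise and fall because only some differences are possible for a given total. Shares of 20%, 30% and 40% mirror 80%, 70% and 60%.

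**4. What an imbalance does.** The shift in the arm difference is imbalance × *B*: 0.20 × 1 = 0.20 SD for 9 v 6, and 0.33 × 2 = 0.67 SD for 10 v 5. The standard error without BSSO is √(2/15) = 0.37 SD. Simulating the planned test at each split (15 per arm):

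| Split | B | False-positive rate | Power when the split works against a true 1.06 SD effect |
|---|---|---|---|
| 9 v 6 | 1 | 5% | 53% |
| 9 v 6 | 2 | 4% | 15% |
| 10 v 5 | 1 | 10% | 39% |
| 10 v 5 | 2 | 17% | 5% |

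At 9 v 6 the false-positive rate does not rise, because the extra spread within arms widens the standard error and offsets the shift. Averaged over all splits it is 4.9% (*B* = 1) and 5.1% (*B* = 2).

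**The case against.** The strongest reply is that randomisation already handles this. BSSO is balanced on average, the ANOVA error term covers chance differences, and overall type I error holds at about 5%. That stands. A reader might infer that the oedema result would simply reflect which arm drew more two-jaw operations, or that any sizeable imbalance would pass for an effect of technique. The plan does not support either inference: a 20-point imbalance, though common at 15 per arm, does not raise the false-positive rate.

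Second, whole-face volume is not in the plan. The region is merely unstated, and if the clinic measures only the nasolabial area most of the concern disappears. That also stands, and is why the conclusion is conditional. It does not remove the point, because nothing in the document commits the trial to such a region.

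Third, a reader might extend the point to every outcome. The seven measurements lie at the nose and upper lip, where a mandibular osteotomy should matter less. For the ROE satisfaction score the document gives no ground to expect a BSSO effect, and none is claimed.

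Fourth, the absence of stratification is read from silence, since no randomisation method is described at all. This is fair for the allocation. It is not fair for the analysis, where one-way ANOVA is a stated choice that leaves BSSO out.

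**Conclusion.** The concern holds as one of precision, confined to the oedema volume and mainly its early visits. If the volume includes the lower face, pooling the two kinds of operation without adjustment can mask a technique effect. At 15 per arm and a 50% BSSO share, power of 80% falls to about 77%, 70% or 50% for a BSSO effect of 0.5, 1 or 2 SD, and adjustment restores nearly all of it. The false-positive risk rises to 10–17% (effect 1–2 SD) only at a split of about 10 v 5; an imbalance of that size or larger has a 2–14% chance at 15 per arm, and about 2% or less at 25. It is not a systematic bias. The BSSO share, its effect and the inclusion of the lower face are all assumptions, so these are ranges and not estimates for this trial. The point is worth acting on because the remedy is cheap. The conflict between 15 and 25 per group must be reconciled in any case; the concern survives at either size, with less chance imbalance at 25.

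**What to change.** 1. **Analysis.** For the oedema volume, replace one-way ANOVA with a linear model containing arm and planned surgery (Le Fort I alone v Le Fort I plus BSSO). Report the number with BSSO in each arm.
2. **Region.** Before unblinding, define the main oedema volume as a nasolabial region bounded by the soft-tissue landmarks already listed ahead of Postoperative Edema Assessment. Those points lie at the nose, glabella and upper lip, so they can bound a nasolabial region but not a midface one. Any larger facial volume should be secondary.
3. **Allocation.** If recruitment has not started, stratify by the same factor, with blocks within each stratum. Patients are enrolled with their operation already scheduled, so the stratum should be known in time. If recruitment has started, steps 1 and 2 still serve.

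The cost is one degree of freedom (about 1.5 points of power if BSSO turns out not to matter), a second allocation list and one region definition in the software. One stratum may be small: at an 80% BSSO share, 0.20 × 30 = 6 patients would have a Le Fort I alone. No surgery or follow-up changes.

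### The plan states two incompatible sample sizes, 30 patients (15 per group) and 25 per group (50 patients), so the recruitment target is not fixed.

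*Combined protocol and SAP*

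**What the plan says.** All the statements about size are in the Selection Criteria section of the combined protocol and SAP.

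- The eligibility paragraph gives a total: "From both groups, a total of 30 patients aged between 18–40years, without acute infection".
- The randomisation sentence repeats the total and splits it: "A total of 30 patients included in the study will be randomly divided into two groups (n=15 each".
- The list which that sentence introduces labels the arms differently: "Group I: Subspinal Le Fort I osteotomy group (n=25" and "Group II Conventional Le Fort I osteotomy group (n=25".

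The Statistical Analysis section names the between-group method, "Comparisons between groups will be performed using one-way ANOVA and Tukey post hoc analysis", but gives no significance level, power, target difference, standard deviation or dropout rate. No primary outcome is designated for sizing. Imaging runs to "Postoperative month 6 (T6", and nothing says that groups may not be compared before then.

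**The concern.** The planned number of patients is a basic parameter of a randomised trial, and here it has two values in consecutive lines. Three things follow.

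- The precision and power of every comparison are unknown in advance, because they depend on which number is used.
- A reader of the results cannot tell whether 30 patients is full enrolment or a shortfall of 20, or whether 50 is on target or an overrun.
- Ending recruitment at 30 or at 50 would each agree with the written plan. If that choice were made after looking at results, the false-positive rate would rise, and the plan as written could not show that this had not happened.

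**Working it through.** **Inputs from the plan (Selection Criteria).** Total 30, stated twice; 15 per group, stated once; 25 per group, stated once for each of two groups.

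**Step 1: do the figures agree?**
- 15 + 15 = 30, which matches the stated total.
- 25 + 25 = 50, which exceeds it by 50 − 30 = 20 patients, and 20/30 = 67%.

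**Step 2: could 50 be 30 inflated for dropout?** With N/(1 − d), rounded up:

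| Dropout d | 30/(1 − d) |
|---|---|
| 10% | 34 |
| 20% | 38 |
| 30% | 43 |
| 40% | 50 |

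Only 40% dropout turns 30 into 50, and the plan states no dropout rate. The text also says that the 30 are the patients being randomised, so 30 cannot be read as the number left for analysis.

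**Step 3: could 30 and 50 count different things?** No. The sentence with 15 per group introduces the list with 25 per group, and both describe the same two randomised groups. The plan gives no separate counts of patients screened, enrolled and analysed.

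**Step 4: what difference does the choice make?** The plan gives no inputs for this step. The assumptions are mine: two-sided 5% level, one outcome, equal groups, differences in SD units. With two groups, one-way ANOVA is equivalent to the two-sided two-sample t-test, so t-test formulas apply to the stated method.

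- 95% confidence interval half-width = t(0.975, 2n − 2) × √(2/n), in SD units.
- Power for a difference d comes from the noncentral t distribution with 2n − 2 degrees of freedom and noncentrality d × √(n/2).
- The detectable difference is the d at which that power equals 80%.

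| Quantity | 15 per group | 25 per group |
|---|---|---|
| 95% CI half-width | 0.748 SD | 0.569 SD |
| Difference detectable with 80% power | 1.060 SD | 0.809 SD |
| Power at 0.5 SD | 26% | 41% |
| Power at 0.8 SD | 56% | 79% |
| Power at 1.0 SD | 75% | 93% |
| Power at 1.2 SD | 89% | 99% |

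**Step 5: what if the result decided which target applied?** Null trials were simulated on one outcome. Each was tested at the 5% level with 15 per group and, if not significant, tested again with 25 per group. The proportion significant at either test was 0.079 in 100,000 trials and 0.0798 in a separate run of 400,000, so about 8% against a nominal 5%.

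**The case against.** The strongest reply is that this is a labelling slip and the size is not truly undefined. Three statements agree on one design: the total of 30 given twice, and 15 per group. The number 50 is never written; it comes only from adding two labels. That makes 30 the likelier intention. It does not settle the matter, because the label of 25 is repeated for both groups and no calculation supports either figure.

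The second reply is that the plan contains no interim analysis, and an inconsistent label does not by itself raise the type I error. That is correct. The 8% applies only if results are inspected at 30 and recruitment continues because of them, and nothing in the plan says this is intended. The direct harm is an unverifiable target and unknown precision. The inflation is a risk that the wording leaves open.

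The third reply is that the power figures rest on inputs the plan does not give, and that a single-comparison calculation does not describe a trial with seven listed measurements, edema assessment and a patient-reported scale. This also stands. The figures show how much the choice between the two sizes matters; they do not show which size is right.

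**Conclusion.** The concern holds. The current text gives two recruitment targets, 30 and 50, which differ by 67% of the smaller, and nothing in the document reconciles them or says which governs. Because sample size is a figure the whole trial relies on, this must be corrected and should not be passed over as a typing error. The contradiction itself needs no assumption. Its consequences, a detectable difference of 1.06 against 0.81 SD and power of 56% against 79% at 0.8 SD, assume a two-sided 5% test of one outcome. The type I error of about 8% further assumes a results-driven choice between the two targets.

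**What to change.** The sponsor should first confirm the approved number from its own records, then state it everywhere in Selection Criteria.

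- **If 30 was approved**, which the text supports better, change both group labels from n=25 to n=15.
- **If 50 was approved**, change the total of 30 in both places to 50 and the 15 per group to 25.

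Two short additions beside the number would close what the contradiction leaves open:

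- the difference the trial can detect with 80% power at a two-sided 5% level (about 1.06 SD at 15 per group, or 0.81 SD at 25), preferably tied to a named primary outcome, since SD units mean little without one;
- a statement that no between-group comparison is made before the last patient's 6-month visit.

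The cost is a wording correction to the protocol. The stated number or precision may look less favourable once it is written plainly.

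### The plan does not say how allocation is concealed or whether the maxillary movement plan and baseline ROE are fixed before it is opened, so both could be set with the arm known.

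*Combined protocol and SAP*

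**What the plan says.** Study Design describes a "single-center, prospective, randomized, and double-blind trial", run "without making any changes to the routine orthognathic surgery and postoperative follow-up protocols conducted in our clinic". Selection Criteria states that the included patients "will be randomly divided into two groups (n=15 each"), although the list directly below it gives 25 for each group. That section ends: "Before the operation, all patients will be informed about the type of osteotomy to be performed".

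The text after Selection Criteria adds: "Patients will complete the ROE (Rhinoplasty Outcome Evaluation) scale preoperatively and at 6 months postoperatively". The first 3D image is scheduled for preoperative day 1 (T0). The same part of the document says: "Changes in maxillary position (anterior and/or superior movement) and their effects on nasal tissues will be analyzed". Movement at Point A, PNS, Is and ANS is to be evaluated after the osteotomy. Statistical Analysis names one-way ANOVA with Tukey post hoc comparisons for the groups, and no covariate.

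The document does not say how the sequence is generated, how it is concealed, who holds it, when it is opened, when the surgeon learns the arm, or when the planned movement is decided. Planned movement is not among the recorded variables.

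**The concern.** The trial aims to isolate the effect of the osteotomy technique on nasal soft tissue. By the protocol's own account, the amount and direction of maxillary movement also affect that tissue, and movement is a decision of the surgical team. The operator cannot be blinded to the osteotomy being performed, so the double-blind label does not protect that decision. What would protect it is order: plan first, allocation opened second. The document sets no order.

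If planned movement shifted with knowledge of the arm, the groups would differ in an influence on the outcome other than technique. The stated ANOVA would attribute that difference to technique. Adjusting afterwards for achieved movement would not fully repair this, because achieved movement arises after randomisation and may itself depend on the arm.

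The baseline ROE raises a related problem. It is a patient-reported satisfaction score. If the patient completes it after learning the technique, it is no longer a clean pre-allocation baseline, either for a change score or as a covariate.

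**Working it through.** **1. What is timed against what**

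| Item | Timing given | Tied to allocation? |
|---|---|---|
| Random division into groups | none | – |
| Patient told the technique | before the operation | no |
| Planned maxillary movement | not recorded | no |
| Baseline ROE | preoperative | no |
| First 3D scan (T0) | preoperative day 1 | no |
| Achieved movement | after the osteotomy | necessarily after allocation |

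Every stated time refers to surgery. Disclosure, movement planning and the baseline ROE all fall in the preoperative period, and the text allows them in any order.

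**2. Size, as an illustration only**

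The document has no figure to reproduce here: it gives no SD, effect size, alpha or power. All inputs except the group size are assumptions.

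- Between-arm difference in mean movement caused by knowing the arm: 0.5 to 2 mm (assumed).
- Response of nasal width: 0.2 to 0.4 mm per mm of movement (assumed).
- SD of the change in nasal width: 1.5 mm, varied from 1 to 3 mm (assumed).
- True technique effect: zero (assumed).
- Group size: 15 per arm (Selection Criteria).
- Test: two-sided 5%. With two groups, one-way ANOVA is the two-sample t-test.

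Bias = movement difference × response. Lowest: 0.5 × 0.2 = 0.1 mm. Highest: 2 × 0.4 = 0.8 mm. Midpoints: 1.25 × 0.3 = 0.375 mm.

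False-positive rate = P(|T| > 2.048), where T is noncentral t with 2 × 15 − 2 = 28 degrees of freedom and noncentrality (bias / SD) × √(15/2). For 0.8 mm and SD 1.5 mm the noncentrality is 0.533 × 2.739 = 1.46.

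| Bias (mm), SD 1.5 mm | False-positive rate, 15 per arm |
|---|---|
| 0 | 5.0% |
| 0.1 | 5.4% |
| 0.2 | 6.4% |
| 0.375 | about 10% |
| 0.4 | 10.9% |
| 0.8 | 29.2% |

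The result depends heavily on the SD. At a bias of 0.8 mm the rate is 56% for SD 1 mm, 18% for SD 2 mm and 11% for SD 3 mm.

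At 25 per arm, the other group size in the document, the range at SD 1.5 mm is 5.6% (0.1 mm) to 45.5% (0.8 mm). A larger trial does not dilute this kind of bias; it makes a false finding more likely.

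**3. A second parameterisation**

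Suppose instead that planned movement shifts by 0.5 or 1.0 SD between arms and that movement and outcome correlate at 0.3, 0.5 or 0.7 (all assumed). The standardised bias is the product of shift and correlation. At 15 per arm a 0.5 SD shift gives 6.8%, 10.1% and 15.3%, and a 1.0 SD shift gives 12.5%, 26.2% and 45.7%. The pattern is the same: negligible at the low end, serious at the high end.

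**The case against.** The strongest reply is that the document is silent here, and silence does not show a fault. The disclosure sentence concerns patients; it does not say who informs them or on which day. Volunteers come from patients already scheduled for surgery, and routine surgical protocols are unchanged, so planning may well be finished before allocation is opened. This stands to the extent that early surgeon knowledge and steering are not shown. But neither statement fixes an order, so the gap remains.

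A reader might infer several stronger things that the document does not support:

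- *Movement is the main driver of nasal change.* The text says only that its effects will be analysed. It does not rank movement against technique.
- *The surgical team holds the allocation list.* No holder is named, and no list is mentioned.
- *The T0 scan is equally exposed.* It is a 3D image taken under set conditions by one clinician, and there is little plausible way for knowledge of the arm to change it.
- *A false-positive rate of 29% is to be expected.* That figure needs the largest movement difference and the largest response together, at an assumed SD. The midpoints give about 10%, and the low end is close to 5%.
- *Analysing achieved movement is a mistake.* The protocol plans it and it is worth keeping. It cannot stand in for a pre-allocation covariate.

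**Conclusion.** The concern holds as a gap in the design: nothing protects the movement plan or the baseline ROE from knowledge of the arm, and the one movement variable collected comes too late to serve as a baseline covariate. Bias is possible, not demonstrated. Its size cannot be derived from the document; about 5% to 29% at 15 per arm with SD 1.5 mm shows only what would follow if the assumed steering occurred.

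The change should be made because it is cheap now and a pre-allocation movement plan cannot be reconstructed once patients have been treated. Two related matters need separate attention: the conflict between 15 and 25 per group must be reconciled, and telling patients their technique does not fit the double-blind description. The second also leaves the 6-month ROE unblinded, which the change below does not cure.

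**What to change.** State the sequence in the protocol:

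1. Confirm eligibility and consent.
2. Complete the baseline ROE.
3. Record the planned maxillary movement on a dated form.
4. Only then open a concealed allocation, held by an existing person outside the operating team, and inform the patient.

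The T0 scan may stay on preoperative day 1. State how the sequence is generated and concealed.

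In the SAP, replace the unadjusted between-group ANOVA with a comparison adjusted for one prespecified planned-movement variable. At 15 per arm a single variable is preferable to several landmarks and axes, and it should be named before enrolment. Keep the planned analysis of achieved movement as a secondary analysis, labelled as not supporting a causal reading of the technique effect.

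The cost is one form, a custodian for the allocation and some protocol wording. The small downside is that departures from the recorded plan must be documented. The change sets no movement value.
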